13.7 Conditions for Terminating the Study

Premature termination of this study may occur because of a regulatory authority decision, change in opinion of the IRB/EC, or study product safety problems, or at the discretion of GSK CH. In addition, GSK CH retains the right to discontinue development of the experimental denture adhesives at any time.

If a study is prematurely terminated, GSK CH will promptly notify the investigator. After notification, the investigator must promptly contact all participating subjects and should assure appropriate therapy/ follow-up for the subjects. As directed by GSK CH, all study materials must be collected and all CRF's completed to the greatest extent possible. Where required by the applicable regulatory requirements, GSK CH should inform the regulatory authority(ies) and the investigator should promptly inform the IRB/EC and provide the IRB/EC a detailed written explanation of the termination or suspension.

If the IRB/EC terminates or suspends its approval/favorable opinion of a trial, the investigator should promptly notify the GSK CH and provide GSK CH with a detailed written explanation of the termination or suspension.

Upon completion or premature discontinuation of the study, the GSK CH monitor will conduct site closure activities with the investigator or site staff, as appropriate, in accordance with applicable regulations including GCP, and GSK CH Standard Operating Procedures.

15 APPENDICES

15.1 ABBREVIATIONS

The following is a list of abbreviations that may be used in the protocol.

Table 15-1 Abbreviations

Abbreviation	Term
AE	adverse event
ANOVA	analysis of variance
AOB	area over baseline
BDR	blinded data review
BF	Bite force
CI	confidence interval
CMC	Carboxymethyl cellulose
CRF	case report form

[figure not shown]
Property of GSK Consumer Healthcare - Confidential

May not be used, divulged, published or otherwise disclosed without the consent of GSKCH

Abbreviation	Term
EudraCT	European Clinical Trials Database
FDA	Food and Drug Administration (United States)
GCP	Good Clinical Practice
GSK CH	GlaxoSmithKline Consumer Healthcare
ICF	Informed consent form
ICH	International Conference on Harmonisation
IND	investigational new drug
IRB	institutional review board
ISO	International organization for standardisation
PPD	PPD
N/A	not applicable
NSR	Non-significant risk
OHT	Oral hard tissue
OST	Oral soft tissue
PI	principal investigator
SAE	serious adverse event
SOP	standard operating procedure
SPF	Super Poligrip Free
TMJ	Temporomandibular joint
USA	United States of America

15.2 Application Instructions

15.2.1 Maxillary Denture Adhesive Application Instructions for Experimental Adhesives

1. Clean and dry dentures.
2. Apply product directly from primary packaging in long, continuous strips as shown in the diagram, not too close to the denture edge. A total of $1.00 \pm 0.05\text{g}$ (weighed) of denture adhesive will be applied to the upper denture.
3. Have the subject rinse their mouth with potable water and expectorate before inserting the denture.

4. Have subject press dentures into place, hold firmly, and bite down for a few seconds to secure hold.

15.2.2 Maxillary Denture Adhesive Application Instructions for Control Adhesive

1. Clean and dry dentures.
2. Apply product directly from primary packaging in short strips as shown in the diagrams, not too close to the denture edges (3 strips should be applied to the upper denture). A total of $1.00 \pm 0.05\text{g}$ (weighed) of denture adhesive will be applied to the upper denture.
3. Have the subject rinse their mouth with potable water before inserting denture.
4. Have subjects press dentures into place, hold firmly, and bite down for a few seconds to secure hold.

15.2.3 Mandibular Denture Adhesive Application Instructions – to stabilize the mandibular denture only (if required)

1. Clean and dry denture.
2. Apply product in short strips as shown in the diagrams, not too close to the denture edges (2 strips on the lower denture in the posterior regions, a third strip may be applied in the anterior region as needed).
3. Have subjects rinse their mouth with water before inserting dentures.
4. Have subjects press dentures into place, hold firmly, and bite down for a few seconds to secure hold.

Signature Page for 218042 TMF-216101 v2.0

Reason for signing: Approved

Name: PPD

Role: A

nature: PPD

PPD

Signature Page for TMF-216101 v2.0

This will be a single-center, controlled, randomized, single blind (with respect to the examiner performing incisal bite force readings), 4-treatment, 4 treatment-period, cross-over study to evaluate maximum maxillary bite force in a population of full maxillary denture wearers. This research is being done to look at how well three denture adhesives hold the subject's denture in place over a 12-hour study period. Two of the denture adhesives are investigational. The other is a marketed denture adhesive (positive control). The study will also look at how well the subject's denture stays in place over a 12-hour study period when using no adhesive (negative control).

1.1 Study Design

This will be a single-center, controlled, randomized, single-blind (with respect to the examiner performing the incisal bite force (BF) measurements), 4-treatment, 4- period, cross-over study to evaluate the maximum maxillary BF in a population of full maxillary denture wearers. The aims of this study are to investigate the hold properties of two experimental denture adhesives using established maximum incisal BF methodology. A currently marketed denture adhesive will be used as a positive control, whilst use of no adhesive will be employed as a negative control.

1.2 Study Objectives

Objectives	Endpoints
Primary	
To compare the maximum incisal bite force until maxillary denture dislodgement of two experimental denture adhesives to no adhesive over 12 hours	Area over baseline in bite force over 12 hours
Secondary	
To compare the maximum incisal bite force until maxillary denture dislodgement of two experimental denture adhesives to no adhesive for time periods up to 9 hours.	Area over baseline up to 0.5, 1, 3, 6 and 9 hours
Safety	
To assess the local tolerability of two experimental denture adhesives	Treatment emergent adverse events and incidents

1.3 Treatments

The two experimental adhesives being investigated in this study have been formulated to provide denture hold throughout the day. In this study the experimental denture adhesives will be compared to no adhesive for all BF assessments. A marketed denture adhesive with extensive clinical evidence of efficacy, Super Poligrip Free (SPF), will be used as a positive control to assess study validity. All adhesive applications will be applied by clinical site dispensing staff and will be controlled by weight for the maxillary denture only ($1.00\text{g} \pm 0.05\text{grams (g)}$). If subjects also wear a mandibular denture (either full or partial), then SPF can be used to stabilize the mandibular denture if required.

Treatments	
Test Product 1	Experimental Denture Adhesive 1 CCI [REDACTED]
Test Product 2	Experimental Denture Adhesive 2 CCI [REDACTED]
Positive Control	Super Poligrip Free Adhesive Cream (CCI [REDACTED])
Negative Control	No Adhesive

1.4 Sample Size Calculation

Sample size calculations for this protocol were provided by GSK CH.

Sufficient subjects will be screened to randomize at least 45 subjects to ensure that at least 42 evaluable subjects complete the study. A sample size of 42 subjects completing all treatment periods will provide 90% power to demonstrate study success. Study success is defined as achieving both (a) study validity (Super Poligrip Free superior to no adhesive) and (b) superiority of either or both of experimental denture adhesives compared to no adhesive (two primary objectives). Prior clinical data supports a delta of 2.30 lbs for AOB₀₋₁₂, using two-sided t-tests with family wise significance level of 5% based on the Dunnett's adjustment with a 5% significance level assuming a residual standard deviation (square root of within mean square error) of 2.83 lbs. The estimate of residual standard deviation was obtained as the higher of the observed variability from two previous bite force studies conducted at OHRI (GSK studies CCI [REDACTED] [REDACTED]).

2 Planned Analyses

2.1 Interim Analysis

No interim analysis is planned.

2.2 Final Analyses

The final planned primary analyses will be performed after the completion of the following sequential steps:

1. All subjects have completed the study as defined in the protocol.
2. All required database cleaning activities including any external data reconciliation have been completed and database has been locked.
3. All criteria for unblinding the randomization codes have been met and the randomization codes have been distributed.

3 Treatment Assignment

3.1 Randomization

The randomization schedule indicates the treatment order sequence; one of the three adhesives or no adhesive (negative control) to be used for each of the four study periods. The randomization uses a Williams Square layout appropriate for a 4-period / 4-treatment crossover design. The product received by the study site includes actual product information (not coded). Therefore, the randomization schedule uses the same product information. This randomization schedule will be used to dispense study treatments to the subjects. The product names used on the randomization schedule are:

Experimental Denture Adhesive 1	CCI
Experimental Denture Adhesive 2	CCI
Super Poligrip Free Adhesive Cream	
No Adhesive	

Although the study only plans to enroll approximately 45 subjects to ensure that at least 42 evaluable subjects complete the study, the randomization schedule includes treatment order sequences for 60 subjects.

The randomization schedule was provided to the OHRI study coordinator by the unblinded IU statistician.

4 Data Analysis

Data analysis will be performed by PPD

The statistical analysis software used will be SAS version 9.4 in a Windows environment.

Prior to database closure a Blind Data Review Meeting (BDRM) will be conducted in which various aspects of the trial will be discussed and agreed between blinded GSK CH team members.

Except as described below, tables and listings will be produced for all randomized subjects.

4.1 Populations for Analysis

Tables and Listings described in this section will be produced for all randomized subjects.

4.1.1 Subject Disposition

Descriptive statistics (frequency and percentage) will be provided for study completion in Table 1. For subjects who discontinue, descriptive statistics (frequency and percentage) will be provided for the reasons for discontinuation in Table 2.

4.1.2 Protocol Deviations

Protocol deviations will be listed in Listing 1. No formal statistical analyses of protocol deviations will be performed.

4.1.3 Analysis Populations

3 analysis populations are defined.

Population	Definition / Criteria	Analyses Evaluated
Safety	
• All randomized subjects who receive treatment at least once during the study.• This population will be based on the treatment the subject actually received.	
• Study Population• Safety
Intent-To-Treat (Modified) (MITT)	
• All randomized subjects with at least one post baseline assessment of efficacy.• This population will be based on the treatment to which the subject was randomized.• Any subject who receives a treatment randomization number will be considered to have been randomized.	
• Efficacy
Per-Protocol (PP)	
• Subset of the MITT population.• Subjects with a protocol violation that is deemed to affect efficacy assessments in all study periods will be excluded from the PP population.• Subjects with a protocol violation that is deemed to affect efficacy assessments in	
• Efficacy

Population	Definition / Criteria	Analyses Evaluated
	
some (but not all) study periods will be part of the PP population, but their data will be excluded from the period(s) affected by the protocol violation for a PP analysis.
 
• Performed for the primary efficacy variable if the number of subjects evaluable in any of the treatment groups for the MITT and PP populations differs by 10% or more. The decision on whether a PP analysis will be performed will be made prior to study unblinding.	

The numbers of subjects included in each of the analysis populations, and the number excluded from each population broken down by the reason for exclusion will be presented in Table 3.

4.2 Subject Demographics and Other Baseline Characteristics

Demographic and baseline characteristics summary tables will be produced for the MITT population. Because of the crossover design, demographic and baseline characteristics for the MITT will be tabulated overall only, not by treatment. Demographic and baseline characteristics will be tabulated overall and by treatment for the PP population.

4.2.1 Demographic Characteristics

Descriptive statistics (number of subjects, mean, standard deviation (SD), median, minimum and maximum for continuous variables, and frequency and percentage for categorical variables) will be provided for demographic data in Table 4. Categorical demographic variables include sex, race, and ethnicity. Continuous demographic variables include age.

4.2.2 Baseline Characteristics

Descriptive statistics (frequency and percentage) will be provided for baseline data in Table 5. Baseline variables include denture bearing tissue score, Kapur-Olshan Index, and well-made assessment.

4.2.3 General Medical History

Medical history and conditions, surgical history, denture history, concomitant medications, and non-drug treatment will be collected in the study database but will not be reported in tables or listings.

4.3 Analysis of Efficacy

Efficacy analyses will be performed for the MITT population, and if necessary, the PP population.

4.3.1 Primary Efficacy Endpoint

4.3.1.1 Primary Efficacy Endpoint Definition

Incisal bite force (BF) (lbs) will be recorded at hour 0 (baseline, pre-treatment) and at 0.5, 1, 3, 6, 9, and 12 hours post-treatment.

The primary efficacy endpoint is area over baseline (AOB) over 12 hours for BF (denoted by AOB_{0-12}) for each adhesive.

To calculate AOB_{0-12} , first the AUC is calculated from 0 to 12 hours using the trapezoid method using the nominal bite force times; we denote this by AUC_{0-12} . AOB_{0-12} is defined as $(AUC_{0-12})/12$ minus baseline BF. This transformation will return the measurement to the same scale as the original observations whilst also looking at the average amount of improved force over time by subtracting the baseline value. Higher values of AOB demonstrate a stronger BF over time than lower values. Missing readings will be imputed using linear interpolation between pre and post the missing values, if necessary. In the case of more than one missing value or if the 12-hour value is missing, the AOB will be set to missing.

The study validity will first be evaluated by comparing Super Poligrip Free vs no adhesive for AOB_{0-12} . Demonstrating study validity ($p<0.05$ for Super Poligrip Free vs no adhesive) is a prerequisite to making inferences for all other treatment comparisons. If the initial validation step is not achieved, the other treatment comparisons will still be performed and presented but the significance tests will not be formally evaluated. The primary objectives are to compare AOB_{0-12} of the two test experimental adhesives versus no adhesive. Therefore, study success is defined as achieving both (a) study validity (Super Poligrip Free superior to no adhesive) and (b) superiority of Experimental Denture Adhesive 1 compared to no adhesive, or Experimental Denture Adhesive 2 compared to no adhesive, or both.

4.3.1.2 Statistical Hypothesis, Model, and Method of Analysis

Null Hypothesis 1: No difference between Super Poligrip Free and no adhesive for AOB₀₋₁₂.

Alternative Hypothesis 1: Difference (superiority) for Super Poligrip Free compared to no adhesive for AOB₀₋₁₂.

Null Hypothesis 2: No difference between Experimental Denture Adhesive 1 and no adhesive for AOB₀₋₁₂.

Alternative Hypothesis 2: Difference (superiority) for Experimental Denture Adhesive 1 compared to no adhesive for AOB₀₋₁₂.

Null Hypothesis 3: No difference between Experimental Denture Adhesive 2 and no adhesive for AOB₀₋₁₂.

Alternative Hypothesis 3: Difference (superiority) for Experimental Denture Adhesive 2 compared to no adhesive for AOB₀₋₁₂.

An analysis of covariance (ANCOVA) model will be used to analyze AOB₀₋₁₂, with treatment and period as fixed effects; the covariates in this model are the subject level baseline and period level baseline minus subject level baseline. Subject will be included as a random effect. Pairwise treatment comparisons will be obtained as a difference in adjusted means and presented with 95% confidence intervals (CI) and associated p-values. Violations of normality and homogeneity of variance assumptions may be evaluated and if found will be overcome using transformations (e.g. natural logarithm) or performing a non-parametric analysis (Friedman's test). The study validity will first be evaluated by comparing Super Poligrip Free vs no adhesive for AOB₀₋₁₂. The primary objectives are to compare incisal bite forces of Experimental Denture Adhesive 1 and Experimental Denture Adhesive 2 versus no adhesive over 12 hours, AOB₀₋₁₂.

A two-sided 5% significance level will be used for all tests. The comparison of Super Poligrip Free against no adhesive will be performed with no multiple-testing adjustment. The comparisons of the two test products against no adhesive will use a Dunnett adjustment for multiple comparisons against a control.

The ANOVA table from the AOB₀₋₁₂ ANCOVA will be tabulated in Table 6. Adjusted means, standard errors, and 95% confidence intervals for AOB₀₋₁₂ will be tabulated by treatment in Table 7. For differences in AOB₀₋₁₂ between Super Poligrip Free and no adhesive, Experimental Denture Adhesive 1 and no adhesive, and Experimental Denture Adhesive 2 and no adhesive, adjusted differences, standard errors, p-values and 95% confidence intervals will be tabulated in Table 8; 95% CI and p-value for Super Poligrip Free against no adhesive will use with no multiple-testing adjustment; 95% CIs and p-values for the two test products against no adhesive will use a Dunnett adjustment for multiple comparisons against a control. The adjusted differences with 95% confidence intervals for AOB₀₋₁₂ between pairs of treatments from Table 8 will be plotted in Figure 2.

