2.1 Study Rationale

The two experimental denture adhesives require a clinical trial to establish clinical efficacy through the measurement of denture retention in order to support intended claims for either of these adhesives.

The maximum achievable incisal bite force prior to denture dislodgement is a commonly used measure of denture hold for denture adhesives and will therefore be used in this study.

This is a Phase III study that is planned to be performed by a clinical site in the United States of America (USA) with experience in the bite force methodology and equipment.

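### A step-down Dunnett test for the two experimental adhesives would keep the 5% family-wise error and, at the planning values, raise the chance of supporting both from about 86% to 90%; the current rule is valid, so this is an inexpensive improvement and not a correction

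*SAP*

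**What the plan says.** SAP 4.3.1.2 first tests Super Poligrip Free against no adhesive, unadjusted, as a validity step. For the experimental adhesives it then says: "The comparisons of the two test products against no adhesive will use a Dunnett adjustment for multiple comparisons against a control". The level is set by "A two-sided 5% significance level will be used for all tests". The later paragraph of that section, which describes Table 8, adds that "95% CIs and p-values for the two test products against no adhesive will use a Dunnett adjustment". The plot of adjusted differences takes its intervals from that table.

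The SAP uses neither the term single-step nor the term step-down. One Dunnett adjustment that yields both p-values and confidence intervals, with no testing order stated, is in effect single-step.

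Success (SAP 1.4 and 4.3.1.1; Protocol 12.1) requires the validity step plus superiority of one or both experimental adhesives. Protocol 2.1 gives the purpose as evidence "in order to support intended claims for either of these adhesives".

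The protocol is not consistent on multiplicity. Its synopsis says that the primary and secondary tests are unadjusted and that there is no hierarchy between the two adhesives, while its section 12.1 bases the sample size on Dunnett. SAP section 5 does not list the Dunnett rule as a change from the protocol.

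**The concern.** Under the single-step rule each experimental adhesive must pass the two-comparison critical value, even after the other has already been declared superior. Closed testing does not require that. With two hypotheses, the Dunnett bound is needed only for the joint null that neither adhesive works. Once the larger statistic passes it, one hypothesis remains, and that can be tested at the ordinary two-sided 5% level. The step-down test therefore rejects everything that the single-step test rejects, and sometimes more.

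What is at stake is the result for the second product. Each adhesive has its own primary comparison, and Protocol 6.1 says that both are meant to be marketed, so the second result has value even though success needs only one.

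**Working it through.** **Inputs (SAP 1.4 unless noted)**
- Completers: "A sample size of 42 subjects completing all treatment periods will provide 90% power to demonstrate study success".
- Effect: "Prior clinical data supports a delta of 2.30 lbs". The text gives one delta; applying it to all three adhesives is an assumption.
- Variability: "residual standard deviation (square root of within mean square error) of 2.83 lbs".
- Level: two-sided 5%, with an unadjusted validity step and Dunnett for the two experimental comparisons (SAP 4.3.1.2).
- Correlation between comparisons: 0.5, through the shared no-adhesive arm.

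**Basic quantities**
- SE of a difference = 2.83 × √(2/42) = 0.6176 lb.
- Noncentrality = 2.30 / 0.6176 = 3.724.
- Residual df = 168 observations − 42 subjects − 3 treatment − 3 period − 1 within-subject covariate = 119.
- Critical values: unadjusted t 1.980; two-sided Dunnett 2.239 for two comparisons and 2.379 for three.

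Joint probabilities come from 2,000,000 simulated sets of t statistics that share the no-adhesive mean and the residual variance.

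**The plan's own 90%**

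| Reading | Power |
|---|---|
| Success, Dunnett over all three adhesives including the positive control | 89.4% |
| Unadjusted validity step plus one named experimental adhesive, Dunnett for two | 90.2% |
| A single comparison, Dunnett for three | 90.9% |
| SAP rule as written: unadjusted validity step, then either or both, Dunnett for two | 94.5% |

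The stated 90% is therefore reproducible, and it is conservative for the rule that the SAP actually sets.

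**Single-step against step-down, 42 completers, validity step included**

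| Outcome | Single-step | Step-down |
|---|---|---|
| Both experimental adhesives supported | 85.9% | 89.9% |
| A given experimental adhesive supported | 90.2% | 92.2% |
| Study success (either or both) | 94.5% | 94.5% |

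The rows agree with each other. Step-down adds a rejection in 89.9 − 85.9 = 4.0% of trials. By symmetry each adhesive is the weaker one in half of these, which gives the 2.0-point gain for a given adhesive.

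**Family-wise error, validity step certain to pass**
- Both nulls true: 5.0% under either method.
- One null true and the other adhesive strongly effective: 5.0% step-down, 2.7% single-step. The difference is permitted error that the single-step rule leaves unused.

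**Sensitivity of the gain for both adhesives**

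| Assumption changed | Single-step | Step-down | Gain (points) |
|---|---|---|---|
| SD 2.5 lb | 94.7% | 96.5% | 1.9 |
| SD 2.25 lb | 98.3% | 99.0% | 0.7 |
| All 45 randomized subjects complete | 88.9% | 92.2% | 3.3 |
| One experimental adhesive at 2.0 lb | 79.0% | 84.8% | 5.8 |
| One experimental adhesive at 1.7 lb | 66.6% | 74.8% | 8.2 |

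The alternative SDs and effects are assumptions for illustration. Gains are taken from unrounded values. For scale, the single-step rule would need about 46 completers (about 89.7%) to come close to what step-down gives with 42.

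**Where the added rejections fall.** They occur only when the weaker adhesive's t lies between 1.980 and 2.239. At the planning SE that is an estimated difference between 1.980 × 0.6176 = 1.22 lb and 2.239 × 0.6176 = 1.38 lb. In all of these cases the Dunnett interval, estimate ± 2.239 × SE, includes zero.

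**The case against.** The strongest reply is that nothing is broken. The SAP prespecifies a valid adjustment of the same type as the sample-size calculation assumes, and the plan sets no power target for supporting both adhesives. On the criterion it does set, the change gains nothing. This stands, and it limits the point to efficiency.

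A reader might go further and infer that the trial is underpowered, or that it needs to establish both products. The documents do not support either reading. Success is reached with one adhesive, its probability under the SAP rule is above the stated 90%, and Protocol 2.1 speaks of claims for either adhesive.

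The second reply is about reporting. At present Table 8's p-values and intervals agree. Under step-down, each gained rejection sits beside a simultaneous interval that includes zero, and the plot shows the same. The gain and this drawback are the same trials. A sponsor could reasonably prefer agreement to a few points of joint power.

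Third, the single-step form is inferred from the adjusted intervals and not written. If the protocol synopsis governed instead, there would be no adjustment to improve on: unadjusted testing supports both adhesives with probability 90.1%, but its family-wise error is 9.1% when both nulls are true. This does not defeat the point, but the conflict between the documents has to be settled in the same edit.

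**Conclusion.** The point holds as an inexpensive improvement and not as an error. With the SAP's Dunnett rule taken as governing and read as single-step over two comparisons, step-down testing keeps the 5% family-wise error and can only add rejections. The gain of about 4 points for both adhesives, and 2 points for a given one, rests on 42 completers, a true 2.30 lb for each of the three adhesives and a residual SD of 2.83 lb. It shrinks if the SD is lower and grows if one adhesive is weaker. It does not touch the probability of study success.

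**What to change.** Before unblinding:

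1. In SAP 4.3.1.2, state that after the validity step the experimental adhesive with the larger absolute t statistic is compared with the two-comparison Dunnett critical value. If it is significant, the other is tested against no adhesive at unadjusted two-sided 5%; otherwise testing stops.
2. Reword the Table 8 paragraph of that section so that the table gives step-down adjusted p-values with single-step Dunnett simultaneous 95% intervals. The adjusted p-value is the two-comparison Dunnett value for the larger statistic. For the other adhesive it is the greater of that value and its own unadjusted p-value.
3. Add a footnote to Table 8 and to the plot of adjusted differences saying that a comparison can be significant under step-down while its simultaneous interval includes zero.
4. Reconcile the rule with the protocol synopsis, which says no adjustment and no hierarchy, and list the multiplicity rule in SAP section 5.

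The cost is SAP wording and footnotes; the model, data, visits and sample size do not change. The statistical price is the mismatch between p-value and interval in about 4% of trials at the planning values. If the sponsor prefers to avoid that, keeping the current rule is defensible, but the SAP should then say that it is single-step, and item 4 is still needed.
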